10.2 Responsibility for Analyses/In-House Blinding

The statistical analysis of the data obtained from this study will be the responsibility of the MSD Clinical Biostatistics department.

MSD will generate the randomized allocation schedule for study treatment assignment for this protocol and the randomization will be implemented in IVRS/TWRS.

An external DMC will be convened to review accumulating safety data to provide an opportunity to terminate the study early if there are concerns regarding safety. Treatment-level results of the safety analyses will be provided by the external unblinded statistician to the eDMC. The DMC responsibilities and review schedules will be outlined in the DMC charter. The recommendation of the DMC will be communicated to the Joint Executive Oversight Committee (EOC) and, in the event of a recommendation to halt the study early due to safety concerns, to the appropriate regulatory agencies. If the DMC recommends modifications to the design of the protocol or discontinuation of the study, the EOC and possibly other limited numbers of additional Sponsor/MSD personnel may be unblinded to results at the treatment level in order to act on these recommendations.

Participant-level unblinding to support regulatory filing, should one occur before the end of the study, will be restricted to a designated Sponsor/MSD team, who will have no other responsibilities associated with the study. The extent to which individuals are unblinded with respect to the results will be documented. Additional logistical details, revisions to the above plan, and data monitoring guidance will be provided in the DMC Charter.

10.3 Hypotheses/Estimation

Objectives and hypotheses of the study are stated in Section 4.0.

10.4 Analysis Endpoints

Efficacy and safety endpoints that will be evaluated for within- and/or between-treatment differences are listed below. [REDACTED]

10.4.1 Efficacy Endpoints

Primary

Objective Response Rate: The proportion of participants who have a confirmed CR or PR per RECIST 1.1 based on BICR.

Secondary

Progression-free Survival: The time from randomization to the first documented PD per RECIST 1.1 based on BICR or death due to any cause, whichever occurs first. See Section 10.6.1 for the definition of censoring.

Overall Survival: The time from randomization to death due to any cause.

Duration of Response: The time from first documented evidence of CR or PR until PD per RECIST 1.1 as assessed by BICR or death due to any cause, whichever occurs first, in participants who demonstrate CR or PR.

10.4.2 Safety Endpoints

Safety and tolerability will be assessed by clinical review of all relevant parameters including AEs, SAEs, fatal AEs, laboratory tests, and vital signs. Furthermore, specific events will be collected and designated as ECIs as described in Section 9.3.7.

10.5 Analysis Populations

10.5.1 Efficacy Analysis Populations

The analyses of primary efficacy endpoints are based on the intention-to-treat (ITT) population. All randomized participants will be included in this population. Participants will be analyzed in the treatment group to which they are randomized. Details on the approach to handling missing data are provided in Section 10.6.

10.5.2 Safety Analysis Populations

The all participants as treated (APaT) population will be used for the analysis of safety data in this study. The APaT population consists of all randomized participants who received at least one dose of study treatment. Participants will be analyzed in the treatment group corresponding to the study treatment they actually received. For most participants, this will be the treatment group to which they are randomized. Participants who take incorrect study treatment for the entire treatment period will be included in the treatment group corresponding to the study treatment actually received. Any participant who receives the incorrect study medication for one cycle, but receives the correct treatment for all other cycles, will be analyzed according to the correct treatment group and a narrative will be provided for any events that occur during the cycle for which the participant is incorrectly dosed.

At least 1 laboratory or vital sign measurement obtained subsequent to at least 1 dose of study treatment is required for inclusion in the analysis of each specific parameter. To assess change from baseline, a baseline measurement is also required.

10.6 Statistical Methods

10.6.1 Statistical Methods for Efficacy Analyses

This section describes the statistical methods that address the primary and secondary efficacy objectives. [REDACTED] Efficacy results that will be deemed to be statistically significant with Type I error strictly controlled at 5%. Nominal p-values will be computed for other efficacy analyses, but should be interpreted with caution due to potential issues of multiplicity.

10.6.1.1 Objective Response Rate

The stratified Miettinen and Nurminen method [Miettinen, O. and Nurminen, M. 1985] will be used for comparison of ORR between the treatment groups. The difference in ORR and its 95% CI from the stratified Miettinen and Nurminen method with strata weighting by sample size will be provided. The stratification factor (Section 7.3.1) based on tumor histology will be used in the analysis.

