3.3 Benefit/Risk Assessment

NOTE: The results of the final efficacy analysis of this study indicated that the study did not meet the pre-specified endpoint of improvement in objective response rate (ORR) for the combination of pembrolizumab plus epacadostat compared with pembrolizumab plus placebo. As of Amendment 05, epacadostat and matching placebo have been removed from the study. Therefore, the benefit:risk assessment of epacadostat is no longer applicable and has been removed.

It cannot be guaranteed that participants in clinical studies will directly benefit from treatment during participation, as clinical studies are designed to provide information about the safety and effectiveness of an investigational medicine.

[figure not shown]
Despite the substantial improvement in PFS and OS observed with pembrolizumab as compared to SOC platinum doublet chemotherapy in KEYNOTE-024, there remains a need to investigate new treatments which offer the prospect of added benefit for this patient population. Details regarding specific benefits and risks of pembrolizumab treatment for participants in this clinical study may be found in the Investigator's Brochure [IB Edition 15 2017] and Informed Consent Form (ICF).

4. Objectives/Hypotheses and Endpoints

NOTE: As of Amendment 05, epacadostat and matching placebo are removed from the treatment groups. All participants remaining on study will continue on open-label pembrolizumab monotherapy. The study will therefore stop collecting efficacy endpoints.

In all randomized participants with treatment-naïve, stage IV NSCLC, highly expressing PD-L1 (TPS \geq 50%):

Objective/Hypothesis	Endpoint
Primary	

 • To compare ORR of the combination of pembrolizumab plus epacadostat versus pembrolizumab plus placebo. • Hypothesis (H1): The combination of pembrolizumab plus epacadostat has superior ORR compared to pembrolizumab plus placebo. 	
 • ORR is defined as the proportion of participants who have a confirmed CR or PR per RECIST 1.1 based on BICR.

This study will be considered to have met its success criteria if pembrolizumab plus epacadostat is superior to pembrolizumab plus placebo in ORR.
	
Secondary	

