Sample Size and Power	The planned sample size is approximately 148 participants with 74 participants in each arm. For the ORR test, based on all patients randomized with minimum 18 weeks of follow-up, the study has 81.7% power to detect a 20-percentage point difference in ORR for pembrolizumab+ epacadostat vs pembrolizumab+ placebo at $\alpha=5\%$ (one-sided).

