10.6.1.2 Progression-free Survival

The non-parametric Kaplan-Meier method will be used to estimate the PFS curve in each treatment group. The treatment difference in PFS will be assessed by the stratified log-rank test (based on the stratification factors defined in Section 7.3.1). A stratified Cox proportional hazard model with Efron's method of tie handling will be used to assess the magnitude of the treatment difference (ie, the HR) between the treatment arms. The HR and its 95% CI from the stratified Cox model with Efron's method of tie handling and with a single treatment covariate will be reported. The stratification factor (Section 7.3.1) based on tumor histology will be applied to both the stratified log-rank test and the stratified Cox model.

Since disease progression is assessed periodically, PD can occur any time in the time interval between the last assessment where PD was not documented and the assessment when PD is documented. For the primary analysis, for participants who have PD, the true date of disease progression will be approximated by the date of the first assessment at which PD is objectively documented per RECIST 1.1 (based on BICR), regardless of discontinuation of study drug. Death is always considered as a confirmed PD event.

In order to evaluate the robustness of the PFS endpoint per RECIST 1.1 based on BICR, two sensitivity analyses with a different set of censoring rules will be performed. For the first sensitivity analysis, participants who miss more than one disease assessment (with or without a subsequent death or progression) are censored at the last disease assessment prior to missing visits. The second sensitivity analysis handles participants who discontinue treatment or initiate an anticancer treatment subsequent to discontinuation of study-specified treatments differently from the primary analysis. The censoring rules for primary and sensitivity analyses are summarized in [Table 10](#). If a participant meets multiple criteria for censoring, the censoring criterion that occurs earliest will be applied.

Table 10 Censoring Rules for Primary and Sensitivity Analyses of Progression-free Survival

Situation	Primary Analysis	Sensitivity Analysis 1	Sensitivity Analysis 2
No PD and no death; new anticancer treatment is not initiated	Censored at last disease assessment	Censored at last disease assessment	Censored at last disease assessment if still on study therapy; progressed at treatment discontinuation otherwise

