10.8 Multiplicity

The overall Type I error rate is strictly controlled at 5% (one-sided) by fixed sequence, a closed-testing procedure. The closed testing procedure will be applied to the primary hypothesis of ORR first. If the primary hypothesis is rejected at the $\alpha=5\%$ level (one-sided), then testing will continue to the key secondary hypothesis of PFS. Nominal p-value for each endpoint will be reported, where applicable, regardless of the outcome of the closed testing procedure dictated by the multiplicity strategy.

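### Is a 95% confidence interval the wrong companion to a one-sided 5% test of ORR and PFS?

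*Protocol*

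**What the plan says.** Protocol Section 10.8 fixes the decision rule: "The overall Type I error rate is strictly controlled at 5% (one-sided) by fixed sequence, a closed-testing procedure". If ORR is rejected, "then testing will continue to the key secondary hypothesis of PFS". Section 4 ties success to ORR alone: "This study will be considered to have met its success criteria if pembrolizumab plus epacadostat is superior to pembrolizumab plus placebo in ORR".

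On estimation, Section 10.6.1.1 states for ORR: "The difference in ORR and its 95% CI from the stratified Miettinen and Nurminen method with strata weighting by sample size will be provided". Section 10.6.1.2 does likewise for PFS, where "The HR and its 95% CI from the stratified Cox model with" a single treatment covariate is to be reported. The sSAP repeats both in 3.6.1.1 and 3.6.1.2. Neither document plans a 90% interval or a one-sided 95% bound in its visible text.

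Section 10.8 also provides for p-values: "Nominal p-value for each endpoint will be reported, where applicable, regardless of the outcome of the closed testing procedure".

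**The concern.** A two-sided 95% interval excludes the null value when the one-sided p-value is below 0.025. The trial's threshold is 0.05. The interval that matches the test is therefore the two-sided 90% interval, or equivalently a one-sided 95% bound.

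For ORR the link is tight, because Table 12 of the protocol assigns both testing and estimation to the stratified Miettinen and Nurminen method. Any ORR result with one-sided p between 0.025 and 0.05 would meet the success criterion and be printed beside an interval that spans zero. A reader used to two-sided 5% testing could take that interval as evidence of failure. Section 10.6.1 adds to the risk by giving the 5% level without naming a side. At stake would be how clearly a positive result reads.

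**Working it through.** **Inputs.** 74 per arm (Section 10.1, Table 9: "The planned sample size is approximately 148 participants with 74 participants in each arm"); ORR of 50% against 70%, and 95 PFS events for a hazard ratio of 0.6 (Section 10.9.1); one-sided alpha 0.05 (Section 10.8). The 95% CI is taken as two-sided, which the text does not state. The ORR check is unstratified, because the histology split is not given.

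**1. Reproduce the stated power.**

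ORR, normal approximation:
- Null SE = √(2 × 0.6 × 0.4 / 74) = 0.0805
- Alternative SE = √((0.25 + 0.21) / 74) = 0.0788
- Power = Φ((0.20 − 1.645 × 0.0805) / 0.0788) = Φ(0.856) = 80.4%

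This is the sSAP figure. Exact enumeration of the Miettinen and Nurminen test gives 81.5%, close to the protocol's 81.7%. The two documents differ on this figure, but the difference does not bear on the present question.

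PFS:
- SE(log HR) = 2/√95 = 0.205
- Power = Φ(0.511/0.205 − 1.645) = 80.1%, against the stated 80%

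Both designs reproduce at one-sided 5%. At two-sided 5% the ORR power would be 70.4% and PFS would need 121 events.

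**2. Locate the ORR band.** With pooled rate p̄, the test statistic is z = d / √(p̄(1 − p̄) × (2/74) × (148/147)). For 47 against 37 responders, d = 10/74 = 0.135 and p̄ = 84/148 = 0.568, so z = 0.135/0.0817 = 1.654. With 37/74 in control:

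| Experimental responders | Difference (points) | One-sided p | 95% CI | 90% CI |
|---|---|---|---|---|
| 46 | 12.2 | 0.069 | −3.9 to 27.6 | −1.3 to 25.2 |
| 47 | 13.5 | 0.049 | −2.5 to 28.9 | 0.1 to 26.5 |
| 48 | 14.9 | 0.034 | −1.1 to 30.1 | 1.5 to 27.8 |
| 49 | 16.2 | 0.023 | 0.3 to 31.4 | 2.8 to 29.0 |

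The band is 47 and 48 responders.

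**3. How often it occurs.** Exact binomial enumeration, 74 per arm:

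| True ORR, control vs experimental | Success at one-sided 5% | 95% CI above zero | In the band | Share of successes |
|---|---|---|---|---|
| 50% vs 70% | 81.5% | 71.6% | 9.9% | 12% |
| 50% vs 65% | 59.2% | 47.5% | 11.7% | 20% |
| 50% vs 60% | 33.6% | 24.8% | 8.8% | 26% |
| 50% vs 50% | 4.6% | 2.9% | 1.7% | 37% |

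**4. PFS.** With 95 events, significance needs an observed hazard ratio of at most exp(−1.645 × 0.205) = 0.714. A 95% CI below 1 needs at most exp(−1.960 × 0.205) = 0.669. At a true hazard ratio of 0.6 the probabilities are 80.1% and 70.2%, a gap of 9.9 points. This ignores the ORR gate and is approximate, since the test is log-rank and the interval comes from a Cox model.

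**5. What a 90% interval would add.** It can be recovered closely from what is already reported, because 1.645/1.960 = 0.839. For 47 against 37, shrinking each arm of the 95% interval by that factor gives:
- lower limit 13.5 − 0.839 × 16.0 = 0.1
- upper limit 13.5 + 0.839 × 15.4 = 26.4

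The direct 90% limits are 0.1 and 26.5. For the hazard ratio the same scaling on the log scale is exact for a Wald interval.

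**The case for a change.** The strongest case for a change is that the mismatch follows from the plan itself and could have been foreseen before any data. Under the sponsor's own alternative about one success in eight would carry an interval spanning zero, and the share rises as the true effect shrinks. The matching interval costs one line per endpoint. It would also help after a negative result, since its upper limit is the one-sided 95% bound on the benefit still plausible.

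The arithmetic stands. The inference that the trial would contradict itself does not. A one-sided p of 0.049 and a 95% interval of −2.5 to 28.9 points are two correct statements at two confidence levels. No passage makes exclusion of zero by the interval a criterion for anything, and the p-value is available to set against the pre-stated alpha. For PFS, a 90% Cox interval would not be certain to agree with the log-rank test, so there the remedy would narrow the gap without closing it.

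The cut-offs are also illustrative. With assumed equal histology strata (15 or 20 squamous per arm) the cut-offs of 47 and 49 hold. With a mild imbalance (13 against 17 squamous), 47 against 37 responders gives a one-sided p of about 0.03 to 0.07, depending on where the responders fall.

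**Conclusion.** No change follows. The observation is true: the interval level (95%, two-sided) and the test level (5%, one-sided) differ, and in the unstratified illustration the difference would show in 9.9% of trials at 50% against 70%. But it touches presentation only. Following the plan as written gives a valid test, a valid interval and a clear decision rule; Type I error and power stay as designed.

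A 95% interval is a fair choice for an estimate. It matches the level used for the subgroup effects in Section 10.10 and for the earlier trial results quoted in Section 3.1, so effects can be compared at one level. Anyone who wants the 90% limits can obtain them closely from those reported.

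The point also had no practical effect on the success criterion. The note opening Section 10 records that the final analysis (data cutoff 10-JAN-2019) did not meet the ORR endpoint. No positive verdict exists for an interval to sit awkwardly beside, and the fixed sequence stops before a formal PFS claim.

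This rests on reading the 95% CI as two-sided, on unstratified calculations with 37/74 control responders for the cut-offs, and on exactly 95 events for the PFS limits.

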10.6.1.2 Progression-free Survival

The non-parametric Kaplan-Meier method will be used to estimate the PFS curve in each treatment group. The treatment difference in PFS will be assessed by the stratified log-rank test (based on the stratification factors defined in Section 7.3.1). A stratified Cox proportional hazard model with Efron's method of tie handling will be used to assess the magnitude of the treatment difference (ie, the HR) between the treatment arms. The HR and its 95% CI from the stratified Cox model with Efron's method of tie handling and with a single treatment covariate will be reported. The stratification factor (Section 7.3.1) based on tumor histology will be applied to both the stratified log-rank test and the stratified Cox model.

Since disease progression is assessed periodically, PD can occur any time in the time interval between the last assessment where PD was not documented and the assessment when PD is documented. For the primary analysis, for participants who have PD, the true date of disease progression will be approximated by the date of the first assessment at which PD is objectively documented per RECIST 1.1 (based on BICR), regardless of discontinuation of study drug. Death is always considered as a confirmed PD event.

In order to evaluate the robustness of the PFS endpoint per RECIST 1.1 based on BICR, two sensitivity analyses with a different set of censoring rules will be performed. For the first sensitivity analysis, participants who miss more than one disease assessment (with or without a subsequent death or progression) are censored at the last disease assessment prior to missing visits. The second sensitivity analysis handles participants who discontinue treatment or initiate an anticancer treatment subsequent to discontinuation of study-specified treatments differently from the primary analysis. The censoring rules for primary and sensitivity analyses are summarized in [Table 10](#). If a participant meets multiple criteria for censoring, the censoring criterion that occurs earliest will be applied.

Table 10 Censoring Rules for Primary and Sensitivity Analyses of Progression-free Survival

Situation	Primary Analysis	Sensitivity Analysis 1	Sensitivity Analysis 2
No PD and no death; new anticancer treatment is not initiated	Censored at last disease assessment	Censored at last disease assessment	Censored at last disease assessment if still on study therapy; progressed at treatment discontinuation otherwise
No PD and no death; new anticancer treatment is initiated	Censored at last disease assessment before new anticancer treatment	Censored at last disease assessment before new anticancer treatment	Progressed at date of new anticancer treatment
No PD and no death; ≥ 2 consecutive missed disease assessments	Censored at last disease assessment	Censored at last disease assessment prior to ≥ 2 consecutive missed visits	Censored at last disease assessment
PD or death documented after ≤ 1 missed disease assessment	Progressed at date of documented PD or death	Progressed at date of documented PD or death	Progressed at date of documented PD or death

Situation	Primary Analysis	Sensitivity Analysis 1	Sensitivity Analysis 2
PD or death documented at any time after ≥ 2 missed disease assessments	Progressed at date of documented PD or death	Censored at last disease assessment prior to the ≥ 2 missed disease assessment	Progressed at date of documented PD or death
PD=progressive disease			

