8.1 Discontinuation of Study Treatment

NOTE: As of Amendment 05, this section has been updated. Participants will be discontinued from the study after completing the Safety Follow-up Visit.

Discontinuation of study treatment does not represent withdrawal from the study.

As certain data on clinical events beyond study treatment discontinuation may be important to the study, they must be collected through the participant's last scheduled follow-up, even if the participant has discontinued study treatment. Therefore, all participants who discontinue study treatment prior to completion of the treatment period will still continue to participate in the study as specified in Section 2 and Section 9.9.3.

Participants may discontinue study treatment at any time for any reason or be dropped from the study treatment at the discretion of the investigator should any untoward effect occur. In addition, a participant may be discontinued from study treatment by the investigator or MSD if study treatment is inappropriate, the trial plan is violated, or for administrative and/or other safety reasons. Specific details regarding procedures to be performed at study treatment discontinuation are provided in Section 9.1.10.

A participant must be discontinued from study treatment but continue to be monitored in the study for any of the following reasons:

- The participant or participant's legally acceptable representative requests to discontinue study treatment.
- Radiographic disease progression as assessed by the investigator per RECIST 1.1, as outlined in Section 9.2.1 (except if MSD approves treatment continuation).
- Unacceptable adverse experiences as described in Section 7.2.1.
- The participant interrupts study treatment administration for more than 12 consecutive weeks, unless approved with written documentation from MSD.
- The participant has a medical condition or personal circumstance which, in the opinion of the Investigator and/or MSD, placed the participant at unnecessary risk from continued administration of study treatment.
- The participant has a confirmed positive serum pregnancy test.
- Noncompliance with study treatment or procedure requirements.
- Any progression or recurrence of any malignancy, or any occurrence of another malignancy that requires active systemic treatment.
- Completion of 35 treatment administrations (approximately 2 years) with pembrolizumab.

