- Discontinuation of treatment may be considered for participants who have attained a CR by local Investigator assessment and have been treated for at least 8 administrations of pembrolizumab and received at least 2 administrations beyond the date when the initial CR was declared.

For participants who are discontinued from study treatment but continue to be monitored in the trial, see Section 2 and Section 9.9.3 for those procedures to be completed at each specified visit.

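### PFS Sensitivity Analysis 2: the missed-assessment row contradicts the two event rows, and a permitted stop in CR is coded as progression (minor)

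*Protocol*

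**What the plan says.** Protocol 10.6.1.2 defines two sensitivity analyses for BICR-assessed PFS. The second "handles participants who discontinue treatment or initiate an anticancer treatment subsequent to discontinuation of study-specified treatments differently from the primary analysis". The rules are in Table 10, and sSAP 3.6.1.2 Table 2 repeats them cell for cell. The SA2 column reads:

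- Row 1 (no PD, no death, no new anticancer treatment): "Censored at last disease assessment if still on study therapy; progressed at treatment discontinuation otherwise".
- Row 2 (no PD, no death, new anticancer treatment): "Progressed at date of new anticancer treatment".
- Row 3 ("No PD and no death; ≥ 2 consecutive missed disease assessments"): censored at the last assessment.
- Rows 4 and 5 (PD or death documented, with few or many missed assessments): "Progressed at date of documented PD or death".

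The text before the table gives one tie rule: "If a participant meets multiple criteria for censoring, the censoring criterion that occurs earliest will be applied".

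Protocol 8.1 lists an optional stop: "Discontinuation of treatment may be considered for participants who have attained a CR by local Investigator assessment", after at least 8 administrations and at least 2 beyond the initial CR. Section 5.1 refers to the same option.

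**The concern.** There are two separate defects in the SA2 column.

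First, row 3 says nothing about therapy status or new treatment, so it overlaps rows 1 and 2. In the overlap the column can call the same participant an event and a censoring. Two programmers who both follow the table could code that participant differently.

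Second, counting discontinuation as an event is what SA2 is for, but row 1 makes no distinction for the stop in CR that the protocol allows. A participant who stops in CR and stays progression-free gets an event at the stop date. One who stops in CR and later progresses is dated at the later PD. The better course gets the earlier event.

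In the visible text SA2 is the only PFS analysis that recodes discontinuation and new therapy. The investigator-assessed PFS analysis (footnote to Protocol Table 12) changes the assessor, not these rules. SA2 is thus where a reader would look to see whether informative discontinuation affects the PFS result.

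**Working it through.** **Step 1: the nearest stated figure.** Protocol 10.9.1 gives 95 PFS events for 80% power at HR 0.6, one-sided 5%. Schoenfeld: 4(1.645 + 0.842)²/(ln 0.6)² = 4 × 6.183/0.2609 = 94.8, rounded up to 95. The figure reproduces, and nothing below changes it.

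**Step 2: the SA2 column by participant state.** Rows 1 and 2 split everyone without PD or death by whether new treatment began. Taking new treatment to imply being off study therapy, there are six feasible states:

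| New treatment | On therapy | ≥2 missed | Row 1 or 2 | Row 3 | Result |
|---|---|---|---|---|---|
| No | Yes | No | censored | – | clear |
| No | Yes | Yes | censored | censored | agree |
| No | No | No | event at stop | – | clear |
| No | No | Yes | event at stop | censored | **conflict** |
| Yes | No | No | event at new treatment | – | clear |
| Yes | No | Yes | event at new treatment | censored | **conflict** |

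Two of the six conflict. In each, only one of the two rows is a censoring criterion, so the tie rule read literally has nothing to rank. In the primary analysis and Sensitivity Analysis 1, the cells for rows 1 to 3 are all censorings, and the rule works there.

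**Step 3: could the cases arise by the cutoff?** Enrollment closed on 05-SEP-2018 (Protocol 5.2) and the cutoff was 10-JAN-2019 (Protocol 10), so minimum follow-up was 127 days.

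- *Two missed scans.* The current text gives no scan interval. Assumed intervals of 6, 9 or 12 weeks need 84, 126 or 168 days.
- *Stop in CR.* On exact 21-day cycles dose 8 falls on day 7 × 21 = 147, which only participants randomized by 16-AUG-2018 could reach. If every cycle ran 3 days early, the limit of the window in Protocol 9.1.9.1.1, dose 8 falls on day 7 × 18 = 126, which every enrollee could reach.

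Both cases were possible. The documents do not say how many occurred. I take the CR option to have been in force before the cutoff; the Amendment 05 summary for Section 8.1 does not list it as new.

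**Step 4: illustrative size.** Assumptions: 74 per arm; exponential PFS; control median 10.3 months (an earlier trial's pembrolizumab result, Protocol 3.1); uniform accrual over 12 months ending 05-SEP-2018; scans every 9 weeks; PD dated at the next scan; deaths and row 2 not modelled separately; unstratified Cox with Efron ties; 2000 trials per scenario. Overlap cases stop at a uniform time before PD or cutoff and need two further scheduled scans before cutoff. CR stops are event-free at the last scan and stop between day 147 and cutoff. With no affected cases and a true HR of 0.60 the estimate is 0.596.

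| Affected (control, experimental) | Overlap: rows 1–2 govern / row 3 governs | CR stops: as written / exempted |
|---|---|---|
| True HR 0.60: (2,2) | 0.616 / 0.595 | 0.610 / 0.597 |
| (2,4) | 0.666 / 0.587 | 0.670 / 0.600 |
| (4,2) | 0.593 / 0.609 | 0.573 / 0.600 |
| True HR 1.0: (2,2) | 0.997 / 0.996 | 0.996 / 0.996 |
| (2,4) | 1.053 / 0.990 | 1.075 / 1.006 |
| (4,2) | 0.963 / 1.025 | 0.942 / 1.006 |

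At true HR 0.60, I varied the control median (8, 10.3, 13 months), accrual (8, 12, 14 months) and scan interval (6, 9, 12 weeks) over 27 combinations of 500 trials. The overlap shift (first value minus second) ranged from +0.014 to +0.034 for (2,2), +0.057 to +0.125 for (2,4) and −0.020 to −0.013 for (4,2). The CR shift ranged from +0.007 to +0.026, +0.050 to +0.108 and −0.029 to −0.025.

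**The case against.** The strongest reply is that the intended reading is evident. Missed assessments are the subject of Sensitivity Analysis 1. SA2 departs from the primary analysis only for discontinuation and new therapy, and its row 3 cell is identical to the primary one, so it looks like an unchanged default. This largely stands: the stated purpose does imply that rows 1 and 2 govern. The table does not say so, however, and read loosely as earliest date wins, the tie rule would censor anyone whose last scan came before the stop, which works against that purpose.

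The second reply is that coding every stop as an event is a deliberate stress test, that the primary analysis already censors CR stops, and that the stop-date versus PD-date asymmetry applies to every discontinuer. The first two parts stand, and a reader who inferred that the event-at-discontinuation rule is itself an error would be wrong. For other stops the rule guards against hidden failure. A stop allowed because of CR is a favourable outcome, so that rationale does not reach it. A local-investigator CR in a BICR analysis is a fair worry, but the exception uses only the reason for stopping; PD stays per BICR.

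Third, the counts in the simulation are assumed. With the roughly 55 events these assumptions give, the standard error of the log HR is about 0.28. The (2,4) overlap gap is ln(0.666/0.587) = 0.126, under half of that. This stands.

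**Conclusion.** Both defects are in the text as written, and the sSAP repeats them. The severity is minor. SA2 is one sensitivity analysis of a secondary endpoint. Under the fixed sequence in Protocol 10.8, PFS is only nominal because ORR was not met. The ORR test, the primary PFS rule and the 95-event figure are unaffected. The effect is small when few participants are affected and the arms are balanced. It is noticeable mainly when counts differ between arms, and it can go in either direction. No passage gives the counts or suggests imbalance.

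Three stronger inferences are not supported:

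- That the plan has no precedence rule at all. It has one, and it settles the overlap everywhere except SA2.
- That participants who stop because of "Completion of 35 treatment administrations (approximately 2 years) with pembrolizumab" are also miscoded. From the initial protocol (06-JUN-2017) to the cutoff is 583 days, which allows ⌊583/21⌋ + 1 = 28 doses, or ⌊583/18⌋ + 1 = 33 with every cycle 3 days early. Nobody could have completed 35, and efficacy collection has stopped.
- That SA2 is certainly the only planned PFS analysis of this kind. Parts of both plans are redacted, so this holds only for the visible text.

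**What to change.** Change two cells in the SA2 column of Protocol Table 10 and sSAP Table 2:

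- **Row 3:** put before the present rule *Rows 1 and 2 take precedence for participants off study therapy or who started new anticancer treatment; otherwise*.
- **Row 1:** extend the censoring condition with *or if treatment was stopped in CR per Section 8.1*, leaving the rest of the cell as it is. No exception for completing 35 administrations is needed.

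Because the analysis has been run, state in the CSR, by arm, how many participants fell in the overlap or stopped in CR and how each was coded in SA2. Only if any did, present SA2 under the revised rules beside the original, labelled post hoc.

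The cost is a short CSR note and at most one rerun. The primary reason for discontinuation is already to be displayed (Protocol 10.6.3, sSAP 3.6.5). Nothing shows that a stop in CR is its own category there, so finding those cases may need a check of response and dosing dates.
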